Appendix-A: Patient recruitment and follow-up chart

Appendix B: Delineation of patient-treatment in the study intervention arm

Appendix-C: Baseline assessment

Heart failure centre _____

I. Demographic information

Patient name: _____ I.D. Number |_|_|_|_|_|_|_|_|_|_| - |_|

Sex: male/female Birth date: |_|_| - |_|_| - |_|_|_|_|

Land of birth: _____ |_|_|_|_| Year of immigration: |_|_|_|_|

Address: _____ Zip: |_|_|_|_|_|

Home telephone number: |_|_| - |_|_|_|_|_|_|_|_|

Mobile phone number: |_|_|_| - |_|_|_|_|_|_|_|_|

1. Family status:

- a. Married
- b. Widower
- c. Divorced
- d. Bachelor

2. Living condition:

- a. Lives at home
- b. Lives in old-age home
- c. Other, please specify: _____ |_|_|

3. Who are you living with: (allow multiple answers)

- a. With spouse
- b. With son/daughter
- c. With other (non-family member) care-giver
- d. With other person, please specify: _____ |_|_|
- e. Lives alone

4. Number of years of formal education | | | years

5. Are you working?

a. Yes (move to question 7)

b. No

6. Why don't you work?

a. Retired

b. Unemployed

c. Due to ill health, please specify: _____ | | | |

d. Other, please specify: _____ | | | |

7. Do you have a profession?

a. Yes

b. No (move to section II)

8. What is your profession? _____ | | | |

II. Referral to the heart failure centre

1. First visit date to the heart failure centre: | | | - | | | - | | | | |

2. Type of referral:

a. Referred after hospital admission by Maccabi nurse at the hospital

b. Referred by a primary practitioner, within two months after a hospital discharge

c. Referred by a consultant cardiologist, within two months after a hospital discharge

d. Was hospitalized more than 2 months ago, referred by the primary practitioner
(move to section III, question-1)

e. Was hospitalized more than 2 months ago, referred by the consultant cardiologist
(move to section III, question-1)

f. Other, please specify _____ | |

3. Information on the hospitalization that lead to the patient referral (a copy of the discharge summary should be transferred to the Gertner Institute)

3a. Hospital admission date: |_|_| - |_|_| - |_|_|_|_|

3b. Hospital discharge date: |_|_| - |_|_| - |_|_|_|_|

3c. Hospital _____ |_|_|_|_| Discharge ward _____ |_|_|

3d. Discharge diagnoses:

Diagnosis	ICD-9 code
1.	_ _ _ . _ _
2.	_ _ _ . _ _
3.	_ _ _ . _ _
4.	_ _ _ . _ _
5.	_ _ _ . _ _
6.	_ _ _ . _ _
7.	_ _ _ . _ _
8.	_ _ _ . _ _
9.	_ _ _ . _ _
10.	_ _ _ . _ _
11.	_ _ _ . _ _
12.	_ _ _ . _ _

III. Clinical evaluation at baseline: patient history

1. Heart failure aetiology

Secondary	Primary	Mark √ where appropriate. Please note where there is a complex etiology. In this case please indicate which is the primary and which is the secondary aetiology	
		1. Coronary Artery Disease	
		2. Hypertensive Heart Disease	
		3. Pericardial Disease	
		4. Cor pulmonale	
		5. Diabetic	
		6. Congenital Heart Disease	
		7. Cardiomyopathy:	
		7a. Dilated	
		7b. Familial	
		7c. Hypertrophic: Evidence for obstruction? 1. Yes; 2. No	
		7d. Post-myocarditis	
		7e. Alcoholic	
		7f. Restrictive	
		7g. Infiltrative, specify: _____	
		7h. Cytotoxic (Adriamycin)	
		7i. Other, specify: _____	
		8. Valvular Disease:	
		8a. Rheumatic	
		8b. Degenerative	
		8c. Ischemic	
		8d. Atherosclerotic	
		8e. Bacterial endocarditis	

2. Risk Factors

a. Smoking status:

- I. Is the patient a current or past smoker?
 1. Yes, current
 2. Yes, but hasn't smoked during the last 6 months or longer;
 3. No (move to question 3b.)
- II. If positive, how many cigarettes per day? ; if less than 1 cigarette/day, write '00'
- III. Age at smoking initiation: years;
- IV. Overall, how many years has he/she been smoking? years

b. Alcohol consumption

One drink = one can of beer (330cc); or one glass of wine (120 cc); or one shot of spirits (e.g. Vodka, whiskey, cognac) (40 cc)

Number of alcohol units per day: . ; if drinks less than one unit a day write mean number of units per day according to the number of units per week divided by seven. If drinks less than one unit per week, write '00';

c. **Hypertension:**

1. Yes 2. No

d. **Dyslipidaemia:**

1. Yes 2. No

e. **Diabetes**

1. Yes 2. No

f. **Menopause** (for women):

1. Yes 2. No

g. **Chronic obstructive lung disease** (COPD)

1. Yes 2. No

h. S/P **acute myocardial infarction**

1. Yes 2. No

- i. S/P **PCI**
 - 1. Yes 2. No
- j. S/P **CABG**
 - 1. Yes 2. No
- k. **Peripheral vascular disease** (PVD)
 - 1. Yes 2. No
- l. **Stroke/TIA**
 - 1. Yes 2. No
- m. History among first degree relatives:
 - a. Coronary artery disease (<60 years of age for men, or <50 for women);
 - b. Cardiomyopathy;
 - c. Sudden death (<60 years of age for men, or <50 for women);

3. Current chronic medical therapy

Drug	Dose	ATC code
1.	_ _ _ mg/gr/units X _ /day	_ _ _ _
2.	_ _ _ mg/gr/units X _ /day	_ _ _ _
3.	_ _ _ mg/gr/units X _ /day	_ _ _ _
4.	_ _ _ mg/gr/units X _ /day	_ _ _ _
5.	_ _ _ mg/gr/units X _ /day	_ _ _ _
6.	_ _ _ mg/gr/units X _ /day	_ _ _ _
7.	_ _ _ mg/gr/units X _ /day	_ _ _ _
8.	_ _ _ mg/gr/units X _ /day	_ _ _ _
9.	_ _ _ mg/gr/units X _ /day	_ _ _ _
10.	_ _ _ mg/gr/units X _ /day	_ _ _ _

IV. Baseline measurements:

1. Weight |_|_|_|. |_| kg
2. Height |_|_|_|. |_| cm
3. Waist circumference |_|_|_|. |_| cm
4. Blood pressure* |_|_|_|/|_|_|_| mmHg

**-Should be measured while the patient is sitting, after at least 5 minutes' rest, while the patient's arm rests on a horizontal surface at the level of the heart. The cuff should match the patient's arm circumference.*

5. Pulse rate* |_|_|_| min

**-Pulse should be measured at rest, after blood pressure measurement*

6. Pulse regularity:

Regular/ Irregular

V. Blood tests (to be obtained every six months unless otherwise specified)

test	Date (mm/yyyy)	results
Haemoglobin	_ _ _ / _ _ _ _ _	_ _ _ . gr/dL
Creatinine	_ _ _ / _ _ _ _ _	_ _ . mg/dL
Urea	_ _ _ / _ _ _ _ _	_ _ mg/dL
Uric acid	_ _ _ / _ _ _ _ _	_ _ mg/dL
Na ⁺	_ _ _ / _ _ _ _ _	_ _ _ meq/L
K ⁺	_ _ _ / _ _ _ _ _	_ _ _ meq/L
Albumin	_ _ _ / _ _ _ _ _	_ _ . mg/dL
Glucose	_ _ _ / _ _ _ _ _	_ _ _ mg/dL
HbA1c*	_ _ _ / _ _ _ _ _	_ _ _ . %
Total-cholesterol**	_ _ _ / _ _ _ _ _	_ _ _ mg/dL
LDL-cholesterol**	_ _ _ / _ _ _ _ _	_ _ _ mg/dL
HDL-cholesterol**	_ _ _ / _ _ _ _ _	_ _ _ mg/dL
Triglycerides**	_ _ _ / _ _ _ _ _	_ _ _ mg/dL
FT4**	_ _ _ / _ _ _ _ _	_ _ . mcg/dL
TSH**	_ _ _ / _ _ _ _ _	_ mU/mL. _ _
Vit B12**	_ _ _ / _ _ _ _ _	_ _ _ _ pg/mL
Folic Acid**	_ _ _ / _ _ _ _ _	_ _ ng/mL. _ _
Iron**	_ _ _ / _ _ _ _ _	_ _ _ mcg/dL

***-For diabetic patients only**

****-Once a year**

Resting Echocardiographic evaluation:

Date of test: |_|_| - |_|_| - |_|_|_|_|

Echocardiographic evaluation

1. Left atrium diameter	_ _ mm
2. End-diastolic left ventricular diameter (LVEDD)	_ _ mm
3. Intra-ventricular septal thickness	_ _ mm
4. Left ventricular ejection fraction (LVEF)	_ _ %
5. Pulmonary systolic pressure	_ _ mmHg
6. Moderate or severe mitral insufficiency	1. Yes; 2. No;
7. Moderate or severe tricuspid insufficiency	1. Yes; 2. No;
8. Pressure gradient across the aortic valve	_ _ mmHg Valve surface area*: _ _ cm ² *-The pressure gradient should be calculated if greater than 25 mmHg

Six minute walk test: |_|_|_| meter. (Write '000' if not tested; specify the reason for the missing measurement: _____ |_|_|)

Resting ECG:

Date of test: |_|_| - |_|_| - |_|_|_|_|

Findings:

1. QRS width |_|_| mm

Findings (mark \checkmark where appropriate)	No	Yes
2. LBBB	_	_
3. RBBB	_	_
4. Atrial fibrillation	_	_
5. Pathological Q waves that indicate old MI	_	_

VI. Clinical evaluation summary:

1. Is there evidence for high-output heart failure? 1. Yes; 2. No

2. Does the patient have chronic atrial fibrillation? 1. Yes; 2. No

3. Characteristics of the heart failure:

a. Mainly left heart failure; (no or minimal right heart failure);

b. Mainly right heart failure; (no or minimal left heart failure);

c. Combined left and right heart failure;

4. Does the patient have an implantable device?

a. **VVI** pacemaker;

b. Atrial-ventricular pacemaker; **DDD**

c. Biventricular pacemaker; **CRT**

d. Biventricular pacemaker and defibrillator (**CRTD**)

e. Defibrillator without pacing (**ICD**)

f. No defibrillator or pacemaker

5. Recommended medical treatment (treatment plan delivered to the primary practitioner):

Drug	Dose	ATC code
1.	□□□ mg/gr/units X □□/day	□□□□□
2.	□□□ mg/gr/units X □□/day	□□□□□
3.	□□□ mg/gr/units X □□/day	□□□□□
4.	□□□ mg/gr/units X □□/day	□□□□□
5.	□□□ mg/gr/units X □□/day	□□□□□
6.	□□□ mg/gr/units X □□/day	□□□□□
7.	□□□ mg/gr/units X □□/day	□□□□□
8.	□□□ mg/gr/units X □□/day	□□□□□
9.	□□□ mg/gr/units X □□/day	□□□□□

VII. Study eligibility check

Inclusion criteria:

I. For patients discharged from hospital up to two months before assessment for study enrolment:

1. Age 18 years or older
2. The patient was hospitalized for:
 - a. newly diagnosed, acute heart failure, or
 - b. exacerbation of chronic heart failure, or
 - c. heart failure exacerbation complicating hospital admission for another cause;
3. Echocardiographic examination which included evaluation of left ventricular function has been performed up to 3 months prior enrolment evaluation or after hospital discharge for acute coronary syndrome, whichever comes last.
4. The patient has heart failure according to the European Society of Cardiology Guidelines (see definition below).
5. The patient has stage C or D heart failure (see definition below).
6. The patient has NYHA function class II to IV at the time of enrolment assessment (see definition below).

II. For patients recruited more than two months after hospital discharge, referred from the community

1. Age 18 years or older
2. Echocardiographic examination which included evaluation of left ventricular function has been performed up to 3 months prior enrolment evaluation or after hospital discharge for acute coronary syndrome, whichever comes last.

3. The patient has heart failure according to the European Society of Cardiology Guidelines (see definition below).
4. The patient has stage C or D heart failure (see definition below)
5. The patient has at least one of the following criteria:
 - a. Chronic treatment with furosemide >40 mg/d;
 - b. Chronic treatment with two types of diuretic drugs;
 - c. NYHA functional class IV (see definition below).;
 - d. 6-min. walk test<300 m;
 - e. The patient has combined left and right ventricular heart failure;
 - f. The patient had at least two hospital admissions for heart failure exacerbations within the last 12 months;

Exclusion Criteria

1. The patient has other severe morbidity which may compromise his\her survival prospects within the next 3 years, e.g. pulmonary insufficiency, end-stage liver or renal failure, metastatic malignancy.
2. The patient is bed-ridden or has severe functional impairment which is unrelated to heart failure (e.g. paraplegia, amyotrophic lateral sclerosis).
3. The patient is unable to understand or adhere to the study protocol, e.g. unable to understand the telephone instructions given by the nurse, to operate the tele-monitoring equipment, to answer the study questionnaires.
4. The patient has alcohol or drug addiction.
5. The patient is participating in another trial.
6. The patient refuses to participate in this trial or sign an informed consent form.

Definitions

Definition of Heart Failure*:

1. The patient has typical symptoms of heart failure (in rest or during exercise),
and
2. The patient has an objective echocardiographic evidence of cardiac dysfunction (systolic and/or diastolic) at rest, and (in case where the diagnosis is in doubt),
3. The patient has a favourable response to treatment directed to heart failure;

Criteria 1 and 2 should be fulfilled in all patients.

* Ref. Swedberg K, Cleland J, Dargie H, Drexler H, Follath F, Komajda M, et al. Task Force for the Diagnosis and Treatment of Chronic Heart Failure of the European Society of Cardiology. Guidelines for the diagnosis and treatment of chronic heart failure: executive summary (update 2005): The Task Force for the Diagnosis and Treatment of Chronic Heart Failure of the European Society of Cardiology. *Eur Heart J*, 2005; **26**:1115-40.

Heart Failure Stage*

- A. Patients at high risk of developing HF. **(Should not be included in the study)**
- B. Patients who have developed structural heart disease but who have never shown signs or symptoms of HF. **(Should not be included in the study)**
- C. Patients who have current or prior symptoms of HF associated with underlying structural heart disease.
- D. Patients with advanced structural heart disease and marked symptoms of HF at rest despite maximal medical therapy and who require specialized interventions.

* Ref. Hunt SA, Baker DW, Chin MH, Cinquegrani MP, Feldman AM, Francis GS, et al. ACC/AHA Guidelines for the evaluation and management of chronic heart failure in the adult: Executive summary a report of the American College of Cardiology/American Heart Association Task Force on practice guidelines (Committee to revise the 1995 guidelines for the evaluation and management of heart failure). *Circulation*, 2001; **104**: 2996–3007.

NYHA functional classification*

- I. No limitations of physical activity. No heart failure symptoms;
- II. Mild limitation of physical activity. Heart failure symptoms with significant exertion; comfortable at rest or with mild activity;
- III. Marked limitation of physical activity. Heart failure symptoms with mild exertion; only comfortable at rest;
- IV. Discomfort with any activity. Heart failure symptoms occur at rest;

*-Source: The Criteria Committee of the New York Heart Association. Diseases of the Heart and Blood Vessels: Nomenclature and Criteria for Diagnosis. 6th ed. Boston, Mass: Little Brown; 1964.

Informed consent form

- A. The patient signed an informed consent form
- B. The patient refuses to sign an informed consent form → **Not eligible**

Did the patient provide filled questionnaires? (SF-36, PHQ-9)

- A. Yes
- B. No, please specify the reason: _____

The patient's assigned treatment (please specify the randomization result):

- A. The patient is assigned to the control group (end of the questionnaire);

B. The patient is assigned to the study intervention group

The date of the next patient's follow-up visit to the cardiologist at the heart failure center*: - -

*-for clinical purpose, **only** in the study intervention group

Disease stability

- A. The patient's heart failure is stable (next visit within a month or later): →
the patient is transferred to a central call center + tele-monitoring;
- B. The patient's heart failure is unstable (next visit in less than a month): →
disease management will be conducted at the heart failure center until the patient's heart failure is stabilized. When stable, the patient will be transferred for further follow-up at the central call center + tele-monitoring;

Appendix-E: Follow up assessment (every 6 months)

I. Demographic information

Patient name: _____ I.D. Number -

Months* from randomization:

* -Follow-up visits will be conducted every 6 months from randomization

II. Information on hospital admissions (hospital discharge summaries should be transferred to the Gertner Institute)

1. Hospital admission-1 date: |_|_| - |_|_| - |_|_|_|_|

2. Hospital discharge-1 date: |_|_| - |_|_| - |_|_|_|_|

3. Hospital-1 _____ |_|_|_| discharge ward-1 _____ |_|_|

4. Discharge diagnoses for hospital admission-1:

Diagnosis	ICD-9 code*
1.	□□□□ . □□
2.	□□□□ . □□
3.	□□□□ . □□
4.	□□□□ . □□
5.	□□□□ . □□
6.	□□□□ . □□
7.	□□□□ . □□
8.	□□□□ . □□
9.	□□□□ . □□
10.	□□□□ . □□
11.	□□□□ . □□
12.	□□□□ . □□

*-to be coded at the Gertner Institute

To be filled at the Gertner Institute: The patient's heart failure during hospital admission-1 was:

a.) The main cause for hospital admission

b.) Exacerbated during hospital admission for other cause

c.) A non-active diagnosis for a hospital admission due to (provide diagnosis):

_____ ICD-9 code □□□□ . □□

Repeat for each hospital admission within the 6-month period

III. Visits to emergency rooms and acute care services

Date	Referred to*	Referral **cause	Referral results***										

 
  _ _ 	-	 _ _ 	-	 _ _ _ _ 	
 
 dd		mm		yyyy	
 
	_ _	-	_ _	-	_ _ _ _	dd		mm		yyyy	_	_	_
_ _	-	_ _	-	_ _ _ _									
dd		mm		yyyy									

 
  _ _ 	-	 _ _ 	-	 _ _ _ _ 	
 
 dd		mm		yyyy	
 
	_ _	-	_ _	-	_ _ _ _	dd		mm		yyyy	_	_	_
_ _	-	_ _	-	_ _ _ _									
dd		mm		yyyy									

 
  _ _ 	-	 _ _ 	-	 _ _ _ _ 	
 
 dd		mm		yyyy	
 
	_ _	-	_ _	-	_ _ _ _	dd		mm		yyyy	_	_	_
_ _	-	_ _	-	_ _ _ _									
dd		mm		yyyy									

 
  _ _ 	-	 _ _ 	-	 _ _ _ _ 	
 
 dd		mm		yyyy	
 
	_ _	-	_ _	-	_ _ _ _	dd		mm		yyyy	_	_	_
_ _	-	_ _	-	_ _ _ _									
dd		mm		yyyy									

 
  _ _ 	-	 _ _ 	-	 _ _ _ _ 	
 
 dd		mm		yyyy	
 
	_ _	-	_ _	-	_ _ _ _	dd		mm		yyyy	_	_	_
_ _	-	_ _	-	_ _ _ _									
dd		mm		yyyy									

 
  _ _ 	-	 _ _ 	-	 _ _ _ _ 	
 
 dd		mm		yyyy	
 
	_ _	-	_ _	-	_ _ _ _	dd		mm		yyyy	_	_	_
_ _	-	_ _	-	_ _ _ _									
dd		mm		yyyy									

Codes

**-Referred to: 1=acute care service of Maccabi Health Services; 2=hospital emergency room; 3. Other acute care services (MADA)*

***-Referral cause: 1=Exacerbation of heart failure; 2=Other cause, heart failure was an active problem; 3=Other*

****-Referral result: 1=hospital admission; 2=discharge; 3=death*

IV. Clinical assessment

1. Current chronic medical therapy

Drug	Dose	ATC code
1.	□□□ mg/gr/units X □ /day	□□□□□
2.	□□□ mg/gr/units X □ /day	□□□□□
3.	□□□ mg/gr/units X □ /day	□□□□□
4.	□□□ mg/gr/units X □ /day	□□□□□
5.	□□□ mg/gr/units X □ /day	□□□□□
6.	□□□ mg/gr/units X □ /day	□□□□□
7.	□□□ mg/gr/units X □ /day	□□□□□
8.	□□□ mg/gr/units X □ /day	□□□□□
9.	□□□ mg/gr/units X □ /day	□□□□□
10.	□□□ mg/gr/units X □ /day	□□□□□

2. Smoking

I. Does the patient smoke cigarettes?

1. Yes
2. No

II. If positive, how many cigarettes per day, on average? □□□ cigarettes; if less than 1/d write '00'.

III. Did the patient try to quit smoking?

1. Yes
2. No (move to question 3)

IV. Did he/she use the following quitting methods? (allow multiple answers)

1. Nicotine substitutes
2. Bupropion ("Zyban")
3. Smoking-cessation group sessions
4. Other, please specify: _____ □□□

3. Does the patient use the home tele-monitoring equipment?

- a. Yes
- b. No

4. What is the monitoring frequency?

- a. |_|_| times/week
- b. If less than one a week, write |_|_| times/month. If less than Once-a-month, write '00'

5. Why did the patient stop using the tele-monitoring equipment?

- a. Following the doctor/nurse order
- b. Due to technical problems
- c. Forgetfulness
- d. Because it is a nuisance
- e. Other, please specify: _____|_|

V. Follow-up measurements:

- 1. Weight |_|_|_|.|_| kg
- 2. Height |_|_|_|.|_| cm
- 3. Waist circumference |_|_|_|.|_| cm
- 4. Blood pressure* |_|_|_|/|_|_| mmHg

**-Should be measured while the patient is sitting, after at least 5 minutes' rest, while the patient's arm rests on a horizontal surface at the level of the heart. The cuff should match the patient's arm circumference.*

5. Pulse rate* |_|_|_| min

*-Pulse should be measured at rest, after blood pressure measurement

6. Pulse regularity: Regular/ Irregular

VI. Blood tests (to be obtained every six months unless otherwise specified)

test	Date (mm/yyyy)	results
Haemoglobin	_ _ / _ _ _ _	_ _ . _ gr/dL
Creatinine	_ _ / _ _ _ _	_ . _ mg/dL
Urea	_ _ / _ _ _ _	_ _ mg/dL
Uric acid	_ _ / _ _ _ _	_ _ mg/dL
Na ⁺	_ _ / _ _ _ _	_ _ meq/L
K ⁺	_ _ / _ _ _ _	_ _ meq/L
Albumin	_ _ / _ _ _ _	_ . _ mg/dL
Glucose	_ _ / _ _ _ _	_ _ mg/dL
HbA1c*	_ _ / _ _ _ _	_ _ . _ %
Total-cholesterol**	_ _ / _ _ _ _	_ _ mg/dL
LDL-cholesterol**	_ _ / _ _ _ _	_ _ mg/dL
HDL-cholesterol**	_ _ / _ _ _ _	_ _ mg/dL
Triglycerides**	_ _ / _ _ _ _	_ _ mg/dL
FT4**	_ _ / _ _ _ _	_ . _ mcg/dL
TSH**	_ _ / _ _ _ _	_ _ . _ mU/mL
Vit B12**	_ _ / _ _ _ _	_ _ pg/mL
Folic Acid**	_ _ / _ _ _ _	_ _ . _ ng/mL
Iron**	_ _ / _ _ _ _	_ _ mcg/dL

*-For diabetic patients only

**-Once a year

Six minute walk test: meter. (Write '000' if not tested; specify the reason for the missing measurement:)

for the missing measurement:)

Resting ECG:

Date of test: - -

Findings:

1. QRS width mm

Findings (mark  where appropriate)	No	Yes
2. LBBB		
3. RBBB		
4. Atrial fibrillation		
5. Pathological Q waves that indicate old MI		

Was the patient given an implantable device within the last 6 months?

- a. **VVI** pacemaker;
- b. Atrial-ventricular pacemaker; **DDD**
- c. Biventricular pacemaker; **CRT**
- d. Biventricular pacemaker and defibrillator (**CRTD**)
- e. Defibrillator without pacing (**ICD**)
- f. No defibrillator or pacemaker

VII. Clinical evaluation summary and assessment of heart failure severity:

1. Heart failure stage* (mark the appropriate answer)
 - C. Structural heart disease with prior or current symptoms of HF
 - D. Refractory HF requiring specialized interventions

*-Source: Hunt SA, Abraham WT, Chin MH, et al. American College of Cardiology; American Heart Association Task Force on Practice Guidelines; American College of Chest Physicians; International Society for Heart and Lung Transplantation; Heart Rhythm Society. ACC/AHA 2005 Guideline Update for the Diagnosis and Management of Chronic Heart Failure in the Adult: a report of the American College of Cardiology/American Heart Association Task Force on Practice Guidelines (Writing Committee to Update the 2001 Guidelines for the Evaluation and Management of Heart Failure): developed in collaboration with the American College of Chest Physicians and the International Society for Heart and Lung Transplantation: endorsed by the Heart Rhythm Society. *Circulation*, 2005;112(12):e154-235.

2. NYHA functional classification* (mark the appropriate answer)
 - I. No limitations of physical activity. No heart failure symptoms;
 - IV. Mild limitation of physical activity. Heart failure symptoms with significant exertion; comfortable at rest or with mild activity;
 - V. Marked limitation of physical activity. Heart failure symptoms with mild exertion; only comfortable at rest;
 - IV. Discomfort with any activity. Heart failure symptoms occur at rest;

*-Source: The Criteria Committee of the New York Heart Association. *Diseases of the Heart and Blood Vessels: Nomenclature and Criteria for Diagnosis*. 6th ed. Boston, Mass: Little Brown; 1964.

VIII. An update of recommended medical treatment (treatment plan, to be delivered to the primary practitioner):

Drug	Dose	ATC code
1.	□□□ mg/gr/units X □ /day	□□□□□
2.	□□□ mg/gr/units X □ /day	□□□□□
3.	□□□ mg/gr/units X □ /day	□□□□□
4.	□□□ mg/gr/units X □ /day	□□□□□
5.	□□□ mg/gr/units X □ /day	□□□□□
6.	□□□ mg/gr/units X □ /day	□□□□□
7.	□□□ mg/gr/units X □ /day	□□□□□
8.	□□□ mg/gr/units X □ /day	□□□□□
9.	□□□ mg/gr/units X □ /day	□□□□□
10.	□□□ mg/gr/units X □ /day	□□□□□
11.	□□□ mg/gr/units X □ /day	□□□□□

Summary of Changes

Effect of Disease Management on Hospital Admissions and Mortality in Ambulatory Patients with Heart Failure: A Randomized Controlled Trial.

Summary of protocol amendments:

1ST AMENDMENT:

Change in inclusion criteria for patients with heart failure recruited from the community. The change was made 6 months after the beginning of the trial (on February, 18th, 2008).

The inclusion criteria for patients recruited from the community in the 1st version of the protocol were:

Inclusion criteria for patients who have not been hospitalized for heart failure within the first two months:

1. Age 18 years or older;
2. The patient has relevant echocardiographic evaluation* performed within 3 months prior to the first evaluation visit in the heart failure centre;
3. The patient has heart failure according to the ESC guidelines (ref. 17);
4. The patient meets at least **one** of the following criteria:
 - a. Daily furosemide dose greater than 40 mg;
 - b. Chronic treatment with two types of diuretic drugs;
 - c. NYHA functional class IV;
 - d. Six-minute walking distance <300 meter;
 - e. Combined left- and right-heart failure;
 - f. At least two hospital admissions for heart failure within the past 12 months;

**If the patient had an acute myocardial infarction during the 3 months prior the screening visit, an updated echocardiographic evaluation has to be performed even if less than 3 months elapsed from the prior assessment.*

The inclusion criteria for patients recruited from the community in the 2nd version of the protocol were:

Inclusion criteria for patients who have not been hospitalized for heart failure within the first two months:

1. Age 18 years or older;
2. The patient has echocardiographic evaluation that includes LVEF assessment. A relevant evaluation for the study is:

Summary of Changes

- a. Evaluation performed within 3 months prior to the first evaluation visit in the heart failure centre;
 - b. Evaluation performed after hospital discharge for acute myocardial infarction, in case the event occurred less than 3 months prior the evaluation visit;
3. The patient has heart failure according to the ESC guidelines (ref. 17);
 4. The patient has stage C or D heart failure (see ref. below);
 5. The patient has NYHA functional classification III-IV at the time of first evaluation visit.

2ND AMENDMENT:

Initiation of point-of-care BNP assessments at baseline and follow-up visits. The change was initiated in January 1st, 2009, and included all patients in the trial.

The study ended in July, 31st, 2012. Between August 2012 and November 2013 we invested efforts in data cleaning, obtaining missing hospital discharge summaries, and completion of endpoint adjudication. The SAP was created during this period, and was finalized before data analysis. The study protocol contains a section of a preliminary statistical analysis plan.

STATISTICAL ANALYSIS PLAN

for Disease Management trial of Heart Failure Disease

Final version – 4/11/2013

Written by:

[name], [name], [name], [name]

Approved by:	Signature:	Date:
[name]	[name]	5/11/2013
[name]	[name]	7/11/2013
[name]	[name]	5/11/2013
[name]	[name]	5.11.13

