and improvement in health-related quality of life (24). It should be noted that this study did not include a control group.

Study objectives

1. To evaluate the feasibility of a comprehensive program that includes disease management by multidisciplinary teams operating in regional heart failure centres and heart failure nurse specialists operating in a central call centre, and home tele-monitoring of body weight, blood pressure and heart rate among patients with heart failure.
2. To evaluate the effect of this program on:
 - a. Reduction of recurrent hospital admissions due to heart failure;
 - b. Reduction of mortality from all causes;
 - c. Improvement of health-related quality of life
 - d. Improvement of the patients' functional status

The program will also include economic evaluation.

Study hypotheses

- The proportion of patients who will have the primary composite outcome (hospital admission due to heart failure or death from all causes) will be smaller than this proportion among patients assigned to the control treatment during follow-up;
- Health-related quality of life and depression scores will be better than those measured among patients assigned to the control treatment during follow-up (secondary outcome measures);
- The functional status of patients assigned to the disease management will be better than among patients assigned to the control treatment during follow-up (secondary outcome measure);

Study design

Open-label, controlled clinical trial of parallel group design.

Study target population

1,200 adult patients insured by Maccabi Health Services, with heart failure; New-York Heart Association (NYHA) functional class: II-IV

Inclusion criteria

A. Inclusion criteria for patients screened within the first two months after hospital discharge for heart failure (re: index hospitalization):

1. Men and women; age: 18 years or older;
2. The patient has relevant echocardiographic evaluation* performed within 3 months prior to the first evaluation visit in the heart failure centre;
3. The patient was discharged from hospitalization for acute, newly diagnosed heart failure, or exacerbation of existing heart failure, or decompensated heart failure during a hospital admission for other cause (information will be obtained from the discharge summary of the index hospital admission);
4. The patient has heart failure according to the ESC guidelines (ref. 17);

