1.2 Study Design

Open randomized controlled trial, with a parallel-group design and an active control arm.

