1.7 Primary Outcome

First hospital admission for acute exacerbation of heart failure, or death from any cause

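### Nothing in the protocol or SAP keeps the person who classifies the cause of an admission, the judged part of the primary endpoint, from seeing the treatment arm

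*Supplement*

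**What the plan says.** The protocol's Study design section describes an "Open-label, controlled clinical trial of parallel group design", and SAP 1.2 an "Open randomized controlled trial, with a parallel-group design and an active control arm". SAP 1.7 defines the primary outcome as "First hospital admission for acute exacerbation of heart failure, or death from any cause". Death needs no judgement of cause; the admission part does.

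That judgement appears on protocol Appendix E, the six-monthly follow-up form, which carries the patient's name and identity number. Section II notes that "hospital discharge summaries should be transferred to the Gertner Institute" and has the ICD-9 codes entered there. It then gives a box, "To be filled at the Gertner Institute: The patient's heart failure during hospital admission-1 was", with three choices: heart failure was the main cause of admission, "b.) Exacerbated during hospital admission for other cause", or a non-active diagnosis.

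Section IV of the same form asks "Does the patient use the home tele-monitoring equipment", then how often, and why use stopped. The protocol's list of follow-up information says tele-monitoring use is assessed for patients assigned to the intervention.

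Adjudication is named once, at the end of the Summary of Changes. It reports that August 2012 to November 2013 was spent on data cleaning, "obtaining missing hospital discharge summaries, and completion of endpoint adjudication". No committee, criteria, source documents or masking are given.

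**The concern.** Patients, nurses and cardiologists cannot be masked to this intervention. The person who reads a discharge summary and decides whether heart failure caused the admission can be. The form places an item that reveals the arm beside that decision, and the plan does not separate the two.

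The decision leaves room for discretion. A patient with heart failure who is admitted with, say, an infection could fall under any of the three choices. If a coder who knows the arm leans even slightly towards the non-active choice for intervention patients, events leave one arm only. The result is a bias in favour of the programme, and no adjustment in the Cox model of SAP 7.1 can remove it.

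**Working it through.** **1. Is the arm recoverable from the form?** Appendix E has no field naming the arm. Because tele-monitoring use is assessed only in the intervention arm, a completed entry in section IV, items 3 to 5, identifies it. A discharge summary may also mention the programme, and no redaction step is described.

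**2. Is there a safeguard elsewhere?** The places where one would be expected say the following.

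| Place | What it covers |
|---|---|
| Protocol, Potential bias | Selection bias, centre differences, contamination |
| Protocol, Interim analysis for safety | Confidentiality of Data Monitoring Committee data |
| SAP 1.5 | Concealment of allocation at randomization |
| SAP 4.1 and 7.1 | Endpoint and model; nothing on who classifies events |
| Summary of Changes | That adjudication was completed; nothing on how |

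Allocation concealment protects assignment. It does not mask the later classification of events.

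**3. Check of the planning input.** The protocol assumes 33% of usual-care patients re-hospitalized for heart disease by 12 months. With odds ratios 0.58 and 0.67 the intervention rates are 22.2% and 24.8%. A two-proportion normal approximation at two-sided 5% gives these powers for 600:600 and 400:800:
- odds ratio 0.58: 98.7% and 97.7% (stated 99% and 98%)
- odds ratio 0.67: 88.0% and 84.3% (stated 89% and 85%)

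The stated figures are reproduced to within about one point, so 33% is the rate the plan used. The protocol says it has no data for the composite.

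**4. Illustration of what is at stake.** Inputs:
- *n* = 680 per arm: 1,361 randomized, one excluded, 1:1 allocation (SAP 1.11 and 1.5)
- *m* = 18% dead at 12 months (protocol sample-size section), taken as independent of admission (assumption)
- *a* = 33% admitted, the heart-disease rate; the documents give no heart-failure rate, so 25% and 20% are also tried (assumptions)
- *f* = share of intervention-arm admissions wrongly ruled out, all in one direction (assumption)
- no true effect; one-sided 2.5%, as in the protocol's main analysis

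Control composite: 1 − (1 − *a*)(1 − *m*) = 1 − 0.67 × 0.82 = 45.1%.

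Intervention composite: 1 − (1 − *a*(1 − *f*))(1 − *m*).
- *f* = 5%: 1 − 0.6865 × 0.82 = 43.7%, difference *d* = 1.35 points
- *f* = 10%: 1 − 0.703 × 0.82 = 42.4%, difference *d* = 2.71 points

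The standard error, √(2p̄(1 − p̄)/680), is about 2.69 points in both cases. The expected *z* is therefore 0.50 and 1.01. The false-positive chance is approximately Φ(*z* − 1.96), which gives 7% and 17%.

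| Assumed admission rate | *f* = 0 | *f* = 5% | *f* = 10% |
|---|---|---|---|
| 33% | 2.5% | 7% | 17% |
| 25% | 2.5% | 6% | 12% |
| 20% | 2.5% | 5% | 9% |

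**The case against.** A reader might infer that the coder held the allocation, or that the form makes masking impossible. The documents support neither. The box is filled in centrally, and no text says that section IV reaches the coder; printing items in one appendix does not show what a coder was given. A reader might also take the three-way box to be the endpoint decision itself. No text says so. SAP 4.2 separates admissions for acute exacerbation from those for heart failure complications, and the box has no complications category, so the final classification probably used something more. That step may have been masked. What remains is that nothing written requires it.

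The size can be overstated too. Looking at admissions alone, 10% miscoding gives about 26%, but admission alone is not the primary endpoint. The 33% is for heart disease, so it does not show that heart-failure admissions make up most of the composite. The calculation also fixes time at 12 months. With one to five years of follow-up, a patient whose first admission is ruled out may still have a later event, so miscoding often delays an event rather than removing it.

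Finally, all-cause death and all-cause admissions and hospital days are pre-specified secondary endpoints (SAP 4.2, items 1 and 6) and need no coding of cause. That is a real but partial guard. They are not designated as a check on the primary result, and the protocol puts power for mortality at only 32% with 600 per arm.

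**Conclusion.** The concern holds as a missing safeguard on the primary endpoint, not as proof of biased coding. The trial is open-label, an item that reveals the arm shares a named form with the classification of cause, and no text masks the coder or the later adjudication. Death from any cause is unaffected.

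Under the stated assumptions, one-way miscoding of 5% to 10% would lift a nominal 2.5% error for the 12-month composite to about 7% to 17% at a 33% admission rate, and to about 5% to 9% at 20%. The miscoding shares have no basis in the documents. They show only that modest differential coding would matter. That is reason enough to act, because the remedy is cheap relative to what it protects.

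**What to change.** - **Form.** Move the three-way classification and the ICD-9 coding off Appendix E to a separate sheet that carries only the study number, the admission dates and the discharge summary. Remove mentions of tele-monitoring, the call centre and the disease management nurse from the summary first, and withhold the rest of the form from the coder.
- **SAP 4.1.** State that primary-endpoint admissions are those classified by coders masked to arm, and that the coding is locked before allocation is merged. Say who adjudicates, from which documents and by what criteria.
- **Admissions already coded.** The trial has ended, so a new sheet cannot change completed forms. Where the arm was visible, re-classify from redacted summaries, or report the all-cause death and all-cause admission results as a stated sensitivity check on the primary result. If adjudication was in fact masked, saying so in the SAP is enough.

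The cost is clerical: splitting one form and redacting summaries that the institute already receives. The same coders can do the work, so no extra reader is needed. Redaction takes time across 1,360 patients followed for up to five years, re-classification adds a second pass, and some residual unmasking will remain.
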